Appendix 11. Prohibited Concomitant Medications which may Result in Drug-Drug Interaction (DDI)

The prohibited concomitant medications listed below should not be taken with PF-06863135 for the period of time at least equal to the required washout period listed in the table below, and throughout the conduct of the study.

The Pfizer study team is to be notified of any prohibited medications taken during the study. After consulting with the sponsor, the investigator will make a judgement on the ongoing participation of any participant with prohibited medication use during the study.

This list of drugs prohibited for potential DDI concerns with the IMP may be revised during the course of the study with written notification from sponsor, to include or exclude specific drugs or drug categories for various reasons (eg, emerging DDI results for the IMP, availability of new information in literature on the DDI potential of other drugs).

This is not an all-inclusive list. Site staff should consult with the sponsor or designee with any questions regarding potential DDI.

| Drug Category | Drugs | Required Washout Period Requirement |
|-------------------------|---|--|
| CYP3A4 Substrate | alfentanil cyclosporine dihydroergotamine ergotamine fentanyl pimozide quinidine sirolimus tacrolimus | 2 weeks or 5 half-lives whichever is longer |
| CYP2C9 Substrate | phenytoin warfarin | 2 weeks or 5 half-lives whichever is longer |

Investigators should consult the product label for any other medication used during the study for information regarding medication that is prohibited for concomitant use.

Also, investigators should consult the product label for lenalidomide and pomalidomide for information regarding medication that is prohibited for concomitant use during the conduct of Parts 1C/2C and 1D/2D, respectively.

1. AMENDMENTS FROM PREVIOUS VERSION(S)

1.1. Amendment 3

This amendment updates some response endpoint definitions and changes in Protocol Amendment 8. Texts taken directly from the Protocol Amendment 8 dated 06 Jun 2021 are *Italicized*.

1.2. Amendment 2

This amendment incorporates the added subcutaneous administration cohorts in the amended protocol (amendment 2, V.25Apr2018) study design. Discussions of detailed study conduct features are referred to the amendment. Discussions on combination treatment in the original SAP were found not applicable and were removed in this amendment. In this amendment, the interim study monitoring using Bayesian predictive probability is clarified.

2. INTRODUCTION

This document describes the planned statistical analyses for Protocol C1071001 latest amendment, dated 06 Jun 2021. This SAP is meant to supplement the study protocol. This SAP supersedes the statistical considerations identified in the protocol and, where considerations are substantially different, they will be identified as such. Any deviations from this analysis plan will be described in the clinical study report (CSR). Any post-hoc, or unplanned analyses performed that are not specified in this SAP will be clearly identified in the CSR. This plan is developed and finalized prior to database lock of the clinical database. This SAP is written with consideration of the recommendations outlined in the International Conference on Harmonisation (ICH) E9 Guideline (Guidance for Industry: Statistical Principles for Clinical Trials) and on the ICH E3 Guideline (Guidance for Industry: Structure and Content of Clinical Study Reports).

Interim data may be analyzed and reported in an interim CSR at any timepoint (including at the primary completion date [PCD]) before the final ORR collection are complete. The following CSRs will contain any updated data collected after the interim CSR cutoff date.

2.1. Study Design

This is a Phase 1 open-label, multi-dose, multi-center, dose escalation, safety, pharmacokinetic (PK) and pharmacodynamic study of PF-06863135 as monotherapy and in combination with lenalidomide, pomalidomide or dexamethasone in adult patients with advanced MM who have relapsed from or are refractory to standard therapy. This study will be divided into dose escalation/finding part (Part 1) and dose expansion part (Part 2). Part 1 dose escalation/finding (with either monotherapy or combination therapies) in order to determine the recommended Phase 2 dose (RP2D) is further divided into:

- *Part 1 intravenous (IV) monotherapy and Part 1 subcutaneous (SC) monotherapy cohorts as well as Part 1.1 priming and maintenance cohorts.*
- *Part 1C lenalidomide combination, Part 1D pomalidomide combination and Part 1E dexamethasone combination cohorts.*

Part 2 dose expansion phase will be divided into 4 cohorts as follows:

- Part 2A (PF-06863135 as monotherapy).
- Part 2C (PF-06863135 in combination with lenalidomide).
- Part 2D (PF-06863135 in combination with pomalidomide).
- Part 2E (PF-06863135 in combination with dexamethasone).

Approximately 120 patients are expected to be enrolled into Parts 1/1.1, 1C, 1D, 1E and approximately 80 patients are expected to enroll into Part 2. Parts 1C, 1D and 1E will enroll approximately 9-16 patients into each safety cohort. Actual number of patients enrolled will depend on the combination tolerability with lenalidomide, pomalidomide and the number of dose levels that are required to select the combination RP2Ds. Patients from the combination cohorts of Parts 1C, 1D, 1E treated at the dose levels selected for Part 2 may be counted towards the sample size of the corresponding cohorts of Part 2. Parts 2A, 2C, 2D and 2E will enroll approximately 20 patients each.

A modified toxicity probability interval (mTPI) method, targeting a DLT rate of 25% and an acceptable equivalence interval of 20% 30% will be utilized for dose escalation in Part 1. All patients will also be monitored closely for DLTs until the end of Cycle 1. All patients will be monitored for late toxicities following the initial DLT period up to Day 60 from first dose. Once a dose level has been declared safe following the 60-day evaluation, patients at lower dose levels who have completed the 60-day late toxicity observation period may escalate to the next higher dose level, if criteria outlined in Section 3.1.4.1 of the protocol have been met. Additional intra patient dose escalations will also be permitted after a minimal interval of 60 days. No crossover is allowed, however, between patients assigned to monotherapy PF-06863135 and the different combination regimens.

For safety reasons, a staggered enrollment strategy will be applied for Parts 1 and 1.1 at each dose level; the first patient will be dosed on C1D1 and observed for 48 hours. If no safety concerns arise during this 48-hr. period, subsequent patients will be enrolled into the same dose level. All patients in Part 1 and Part 1.1 will be monitored closely for dose limiting toxicities (DLTs, see Section 3.2 of the protocol) during the first 21-day period for weekly dosing and 28-day period for Q2W dosing.

[figure not shown]
Following the initial dose, treatment with investigational product will continue until disease progression, subject withdrawal of consent or unacceptable toxicity occurs. A follow up visit approximately 4 weeks after the last dose for adverse event (AE) and serious AE (SAE) collection will be conducted. If the subject completes the 1 month follow up visit prior to completion of the 60-day long term DLT observation period, a follow up phone call will be completed on Day 60, and no later than Day 65. Patients found to have anti-drug antibodies (ADA) at their final study visit and an ongoing AE possibly related to ADA will be asked to return to the clinic for ADA assessment at approximately 3 month intervals (if feasible given

the underlying disease) until the adverse event or its sequelae return to baseline or stabilize at a level acceptable to the investigator and sponsor.

Following discontinuation of study treatment (unless subjects are lost to follow up, consent is withdrawn, or study is discontinued by the sponsor), survival status will be collected by telephone every 3 months until death, or up to 24 months after first treatment of the last subject, whichever comes first. Subsequent anti-cancer therapies and relevant transplant information will also be collected.

Treatment with investigational product will continue until disease progression, subject refusal or unacceptable toxicity occurs. It is estimated that subjects will remain on treatment for approximately 4-12 weeks (exclusive of survival follow-up). Actual duration can be longer, if a subject derives benefit from study treatment. The last study treatment will be up to 24 months after first treatment of the last patient, and the study would then end after any additional follow-up visits required after the last study treatment.

Figure 1 C1071001 Study Design

2.2. Study Objectives and Endpoint

2.2.1. Part 1 IV and SC monotherapy Dose Escalation, Part 1.1 Priming and Maintenance Dose Escalation and Parts 1C, 1D and 1E Dose Escalation/Finding

Type	Primary Objectives:	Primary Endpoints:
Safety	
 To assess safety and tolerability at increasing dose levels of PF-06863135 as 	
 Number of DLTs following treatment with escalating doses of PF-06863135 as monotherapy and in combination with lenalidomide, pomalidomide, or dexamethasone

	monotherapy and in combination with lenalidomide, pomalidomide, or dexamethasone in successive cohorts of patients with multiple myeloma in order to estimate the Maximum Tolerated Dose (MTD) or Maximum Administered Dose (MAD) and select the Recommended Phase 2 Dose (RP2D).	dexamethasone. DLT is observed up to the end of Cycle 1 in each participant
	Secondary Objectives:	Secondary Endpoints:
Safety	
 To evaluate the overall safety profile. 	
 Adverse Events as characterized by type, frequency, severity as graded by NCI CTCAE version 4.03, timing, seriousness, and relationship to PF-06863135 treatment as monotherapy and in combination with lenalidomide, pomalidomide, or dexamethasone. Laboratory abnormalities as characterized by type, frequency, severity (as graded by NCI CTCAE version 4.03), and timing.
Efficacy	
 To evaluate anti-myeloma activity of PF-06863135 as monotherapy and in combination with lenalidomide, pomalidomide, or dexamethasone. 	
 ORR defined using the International Working Group (IMWG) response criteria for multiple myeloma and is the percentage of participants with best overall confirmed BOR of sCR, CR, VGPR, or PR relative to the appropriate analysis set. Time to event endpoints as follows: 
 TTR defined as the time from date of first dose to the first documentation of objective treatment response (PR, VGPR, CR, or sCR, whichever is earlier in participants with BOR of PR, VGPR, CR or sCR). CRR defined as the proportion of subjects with confirmed stringent Complete Response (sCR) and Complete Response (CR). CBR defined as proportion of subjects with a BOR of sCR, CR (with or without MRD negativity) VGPR, PR, and MR. DOR, defined as the time from the first documentation of OR to the first documentation of objective PD of progression, clinical relapse or to death due to any cause, whichever occurs first. DoCR or sCR, defined as the time from the

		
first documentation of complete response to the first documentation of objective progression, clinical relapse or death due to any cause, whichever occurs first.
 
 • DOSD is defined for patients with stable disease as the time from the first documentation of objective stable disease to the first documentation of objective tumor progression or to death due to any cause, whichever occurs first. • PFS, defined as the time from date of first dose to date of first documentation of objective PD of progression, or death due to any cause (progression as defined by IMWG response criteria for PD). • OS, defined as the time from date of first dose to date of death due to any cause. Subjects are censored at the time of last follow-up. • Rate of patients with no MRD (by lab data) after treatment with PF-06863135 using IMWG MRD criteria
PK	
 • To evaluate single dose and multiple dose PK of PF-06863135 given as monotherapy and in combination with lenalidomide or pomalidomide. Additionally, PK of lenalidomide, pomalidomide, and dexamethasone will be evaluated when combined with PF-06863135 (Parts 1C, 1D, and 1E, respectively). 	
 • Pharmacokinetic parameters of PF-06863135: Cycle 1 Day 1 dose and Cycle 2 Day 1 dose maximum concentration (C_{max}), area under the concentration versus time curve from time zero to the last quantifiable time point prior to the next dose (AUC_{last}) and if data permit, clearance (CL or CL/F), volume of distribution at steady state (V_{ss} or V_{ss}/F), and terminal elimination $t_{1/2}$. • Plasma lenalidomide, pomalidomide, and dexamethasone concentrations at selected time points (Parts 1C, 1D, and 1E, respectively).
Immunogenicity	
 • To evaluate immunogenicity of PF-06863135 as monotherapy and in combination with, lenalidomide, pomalidomide, or dexamethasone. 	
 • Incidence and titers of anti-drug antibodies (ADA) and neutralizing antibodies (Nab) against PF-06863135.
Biomarker	
 • To characterize the impact of PF-06863135 as monotherapy and in combination with lenalidomide, pomalidomide, or dexamethasone, on systemic soluble immune factors. 	
 • Pre- and post-dose quantification of soluble cytokines in serum.

	Tertiary/Exploratory Objectives:	Tertiary/Exploratory Endpoints:
Biomarker	
 Evaluate the effect of PF-06863135 as a monotherapy and in combination with lenalidomide, pomalidomide, or dexamethasone on plasma cell, T and B cell compartments. 	
 BCMA expression on plasma cells in bone marrow, as assessed by multiparameter flow cytometry and immunohistochemistry; Pre- and post-dose levels of soluble BCMA; Enumeration of T, B, and NK subtypes in whole blood and bone marrow by flow cytometry analysis; T-cell immunophenotyping, including but not limited to proliferation and activation markers in whole blood and bone marrow by flow cytometry analysis; T-cell engagement, including but not limited to proliferation and activation markers in bone marrow by immunohistochemistry; The relative expression of RNA transcripts, including but not limited to, those associated with immune activation and immune regulation in bone marrow and peripheral blood; The abundance and diversity of T-cell clones in bone marrow and peripheral blood.
Biomarker	
 To collect banked biospecimens for exploratory research, unless prohibited by local regulations or ethics committee decision. 	
 Collection of banked biospecimens unless prohibited by local regulations or ethics committee decision.

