8.2.2.1. Progression-Free Survival (PFS)

PFS is the time from date of first dose to date of first documentation of PD in a progression or death due to any cause. PD or death after no more than 1 missing tumor assessment or date of first dose will be counted as an event according to the disease assessment date or date of death, as appropriate. The definitions of relapse, clinical relapse and relapse from CR are not to be used in calculation of progression free survival. Subjects will be considered to have progressive disease if they meet the criteria for progression even by a variable that was not considered as a measurable marker at baseline; however, for subjects who had a measurable serum or urine M-spike at baseline, progression cannot be defined by increases in serum FLC alone. In the IMWG criteria, clinical relapse subjects must also meet the criteria for progressive disease shown here to be classified as progressive disease for the purposes of calculating time to progression and progression-free survival.

Clinical relapse will be equivalent to PD. Note that a progression is defined as:

- 2 consecutive assessments of PD,
- or 1 PD as last efficacy assessment followed by permanent treatment discontinuation,

- or 1 PD following treatment discontinuation (EOT for both treatments in combined therapy - Part 1C and Part 1D). If the discontinuation is after PD but before the next response, then it is considered PD. If there are better responses before discontinuation, it is not considered PD to allow for possible pseudo progression from the treatment which is clinically possible and accepted.

The mITT analysis set will be used.

Censoring: Subjects without an event or with an event after 2 or more missed tumor assessments will be censored as described in Table 4. In addition, if a new anti-cancer therapy is started prior to an event, the subject will be censored on the date of the last adequate tumor assessment that documented no progression prior to the start of the new anti-cancer therapy.

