8.2.2.6. Duration of Response (DoR)

DoR is defined, for participants with an objective response per IMWG criteria, as the time from the first documentation of objective response that is subsequently confirmed, until PD per IMWG criteria, or death due to any cause, whichever occurs first. It will be calculated as follows:

$$\text{DoR (months)} = [\text{date of event or censoring} - \text{first date of objective response} + 1] / 30.4375$$

The censoring rules for DoR are as described for PFS in Section 8.2.2.1, except that participants will not be censored for inadequate baseline assessment or for no adequate post-baseline assessment, as only participants with an objective response are included in the analysis of DoR.

If at least 3 participants achieve an objective response and subsequently have an event, DoR will be estimated using the same Kaplan-Meier method as described for PFS in Section 8.2.2.1 and displayed graphically where appropriate. Otherwise, only listings will be provided.

The DoR rate at 3, 6, 9, 12 and 18 months (and in subsequent 6-month increments while there are participants still at risk) will be estimated with corresponding two-sided 95% CIs.

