SD	No Change/Stable Disease: At least one objective status of Stable Disease but not qualifying as any of the above. If radiographic studies were performed there should be no known progressive or new bone lesions. Subjects who had a single response of sCR, CR, VGPR, PR, or MR but no SD response can also confirm SD.
Progressive Disease (PD)	First objective status recoded of Progression. Progression is defined per the IMWG response criteria for Progressive Disease. Clinical relapse will be equivalent to PD. Note that a progression is defined as: 
 • 2 consecutive assessments of PD, • or 1 PD as last efficacy assessment followed by permanent treatment discontinuation, • or 1 PD following treatment discontinuation (EOT for both treatments in combined therapy - Part 1C and Part 1D). If the discontinuation is after PD but before the next response, then it is considered PD. If there are better responses before discontinuation, it is not considered PD to allow for possible pseudo progression from the treatment which is clinically possible and accepted.

CR and sCR: MRD tests should be initiated only at the time of suspected complete response. Confirmation with two consecutive assessments is not required.

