4. All relapse categories require two consecutive assessments made at any time before classification as relapse or disease progression and/or the institution of any new therapy. To confirm response or progressive disease, two discrete samples are required and testing cannot be based upon the splitting of a single sample. In the IMWG criteria, CR subjects must also meet the criteria for progressive disease shown here to be classified as progressive disease for the purposes of calculating time to progression and progression-free survival. The definitions of relapse, clinical relapse and relapse from CR are not to be used in calculation of time to progression or progression free survival. Subjects will be considered to have progressive disease if they meet the criteria for progression by a variable that was not considered measurable at baseline; however, for subjects who had a measurable serum or urine M-spike at baseline, progression cannot be defined by increases in serum FLC alone.
5. For progressive disease, serum M-component increases of ≥ 1 gm/dL are sufficient to define relapse if starting M-component is ≥ 5 g/dL.

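### The SAP gives conflicting event rules for clinical relapse that does not meet IMWG progression (PFS, DoCR and DOR, a Part 2 primary endpoint), and Table 4 conflicts with its own text on events after treatment stops

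*SAP*

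**What the plan says.** **Clinical relapse.** For PFS, SAP 8.2.2.1 first excludes it: "The definitions of relapse, clinical relapse and relapse from CR are not to be used in calculation of progression free survival". It adds that "clinical relapse subjects must also meet the criteria for progressive disease shown here to be classified as progressive disease". It then states: "Clinical relapse will be equivalent to PD". Table 6, under ORR, repeats the equivalence: "Progression is defined per the IMWG response criteria for Progressive Disease. Clinical relapse will be equivalent to PD". Appendix 2 footnote 4 excludes it again: "clinical relapse and relapse from CR are not to be used in calculation of time to progression or progression free survival".

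For DOR and DoCR, SAP 2.2.1 lists clinical relapse as an event; the DOR wording runs "to the first documentation of objective PD of progression, clinical relapse or to death due to any cause, whichever occurs first". SAP 2.2.2 carries that definition into Part 2 as a primary endpoint. Sections 8.2.2.6 and 8.2.2.7 instead follow the patient "until PD per IMWG criteria, or death due to any cause, whichever occurs first". Protocol 9.4 also names only objective progression or death.

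Section 8.2.2.1 defines an adequate post-baseline assessment twice. The paragraph before Table 4 includes Relapse among the qualifying statuses; the definition after Table 5 does not.

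**After treatment stops.** Table 4 is offered as a summary of the 8.2.2.1 rules. Its general progression row and general death row apply before treatment discontinuation and, through footnote 2, up to 28 days after it. Its discontinuation row censors at the last assessment in that window. The text of 8.2.2.1 counts PD or death after no more than one missed assessment, and counts a single PD after discontinuation, with no day limit. For DOR, "The censoring rules for DoR are as described for PFS in Section 8.2.2.1", apart from the baseline and no-assessment rules.

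**The concern.** Two analysts who both follow the SAP can end the same response on different dates, or one can record an event where the other censors. Relapse and PD are not the same set: under SAP Appendix 2, a myeloma-related creatinine rise, hypercalcemia or a hemoglobin fall can establish clinical relapse, and none of these is a PD criterion. No passage ranks the competing rules. The SAP introduction promises to identify substantial departures from the protocol, and protocol section 9 promises an amendment for major changes to primary endpoint definitions. The relapse term in 2.2.1 is not flagged as a departure from protocol 9.4.

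The Table 4 conflict matters because protocol 7.2 has standard-of-care response assessments reported after treatment ends, until progression or new therapy. Events after stopping will therefore be in the database. What is at stake is the DOR, DoCR and PFS estimates.

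**Working it through.** **1. Status of relapse without IMWG PD, rule by rule**

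| Place | Endpoint | Status |
|---|---|---|
| SAP 2.2.1 | DOR, DoCR | Event |
| SAP 2.2.1 | PFS | Not listed (IMWG PD only) |
| SAP 8.2.2.1, earlier statements | PFS | Not an event unless PD criteria are met |
| SAP 8.2.2.1, later statement | PFS | Same as PD |
| SAP 8.2.2.6, 8.2.2.7 | DOR, DoCR | Not named; depends on which PD sentence is followed |
| SAP Table 6 | Best response | Same as PD |
| SAP Appendix 2, footnote 4 | TTP, PFS | Not used |
| Protocol 9.4 | DOR, DoCR | Not named |

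**2. Worked dates.** SAP 8.2.2.6 gives DOR = (event or censoring date − first response date + 1)/30.4375. The dates are hypothetical, with first response on day 60.

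- Relapse day 240, IMWG PD day 330: 181/30.4375 = 5.95 months if relapse counts; 271/30.4375 = 8.90 months if only PD counts.
- Relapse day 240, last earlier assessment day 232, then new therapy and no PD: event at 5.95 months, or censored at 173/30.4375 = 5.68 months.
- Stopped for toxicity day 200, assessed days 226 and 254, PD day 282: the text gives an event at 223/30.4375 = 7.33 months; Table 4 read literally censors at 167/30.4375 = 5.49 months.
- Stopped day 200, assessed day 226, death day 250: event at 191/30.4375 = 6.28 months by the text; censored at 5.49 months by Table 4.

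**3. Inputs for scale.** Protocol 1.2.3.2 reports an ORR of 63.4% (48.1, 76.4) in 41 patients. 26/41 = 63.4%, with Wilson 95% interval 48.1 to 76.4, so there were 26 responders. Median DOR was 11.6 months and follow-up ranged from 0.30 to 24.41 months. Applying 63.4% to the 15 patients in Part 2A gives 9.5 responders, and to the 9 in Part 1D gives 5.7 (this borrows the monotherapy rate). The protocol does not say which relapse rule produced the 11.6 months.

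Assumptions: exponential DOR with hazard λ = ln 2/11.6 = 0.0598 per month, and follow-up uniform on 0.3 to 24.4 months. The chance that a responder has an event is 1 − (e^(−0.3λ) − e^(−24.4λ))/(24.1λ) = 0.48. That is 12.5 events in 26 responders, or 4.8 in 10.

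**4. One relapse-only ending moved from event to censored** (6,000 simulated cohorts, each compared with itself; in brackets, PD documented two months later if still followed)

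| | 26 responders | 10 responders |
|---|---|---|
| Shift in median, 50th percentile (months) | 0.0 (0.0) | 0.0 (0.0) |
| Shift in median, 75th percentile (months) | 0.8 (0.0) | 1.3 (0.6) |
| Median not reached | 7% to 12% (8%) | 20% to 36% (21%) |
| Mean 12-month DOR | 49.1% to 52.0% (49.6%) | 48.9% to 56.7% (50.2%) |

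Section 8.2.2.6 gives a Kaplan-Meier estimate only with at least 3 events. With exactly 3, one of them relapse-only, the rule chosen decides between an estimate and a listing. P(exactly 3) = C(n,3) × 0.48³ × 0.52^(n−3), about 0.14 for n = 10 and 0.31 for n = 6.

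**5. The 28-day wording taken literally.** With 26 responders, 20% stopping while in response and all still assessed, 1.8 of 12.5 events (14%) are lost. The 12-month DOR stays within 0.2 points if the hazard is unchanged after stopping. If the hazard doubles, 2.5 of 13.5 events (19%) are lost and 12-month DOR reads 47.8% instead of 44.4%. Varying only when patients stop moves the 1.8 to between 1.3 and 2.1. A second set of assumptions (24 months' follow-up; independent stopping with median 48, 24 or 12 months) loses 11%, 20% or 34% of events.

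**The case against.** **The equivalence sentence may be a deliberate override of IMWG.** It may be, but the exclusion stands a few sentences earlier in the same section and again in Appendix 2, and nothing says which prevails. It is also fair that Table 6 is a best-response table and not a DOR event rule. The conflict does not depend on it, because 8.2.2.1 carries the same sentence.

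**A reader might infer that only IMWG PD is an admissible ending for DOR.** The documents do not settle that. SAP 2.2.1 and the equivalence sentences support counting relapse; 8.2.2.6, 8.2.2.7 and protocol 9.4 point the other way. What they do support is choosing one rule and stating it everywhere.

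**A reader might infer that Table 4 simply stops counting progression and death 28 days after treatment.** That goes too far. No row says a documented later PD is censored. The text and Table 6 count one PD after discontinuation with no day limit. Table 5 has no censoring reason for stopping treatment. The row for death before the first planned assessment carries no footnote. The defect is a table whose wording conflicts with its text, not a settled 28-day rule.

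**The size is modest and assumed.** This largely stands. The 8-point figure moves 1 of about 4.8 expected events (21%) and supposes that PD is never documented later. The 26-responder set is pooled, whereas 8.2.2 summarizes by dose cohort. At the June 2022 cutoff Part 2A was the only Part 2 cohort with patients. Off-treatment assessments are standard of care only, and events after two or more missed assessments (46 or 60 days) are censored under both readings, so the losses in step 5 assume fuller follow-up than the protocol guarantees.

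**Conclusion.** Both inconsistencies are real and should be fixed before database lock. The relapse conflict is explicit and reaches a Part 2 primary endpoint. The Table 4 conflict is one of wording that, taken literally, can censor PFS and DOR events the text counts.

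The effect on the trial's estimates cannot be determined: the documents give no number of relapse-only endings, no number of responders who stopped while in response, and no statement of the rule behind the reported median. The simulations rest on exponential durations, assumed follow-up and assumed stopping rates, and show scale only. The typical shift in median DOR is 0.0 months, with larger movements possible in small cohorts. The Table 4 reading distorts 12-month DOR appreciably only if risk changes after stopping. ORR is unaffected and no hypothesis test is planned. Nothing here shows that the reported 11.6 months is wrong.

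**What to change.** **Relapse.** Adopt one rule and apply it in SAP 2.2.1, 8.2.2.1, 8.2.2.6, 8.2.2.7 and Table 6. The rule closest to the protocol is IMWG PD or death: delete the equivalence sentence from 8.2.2.1 and Table 6, delete the relapse term from DOR and DoCR in 2.2.1, and report relapse-as-event as a sensitivity analysis. Under this rule give relapse-only patients a named non-response category in Table 6. A separate row would match 8.2.2.3, which already lists clinical relapse apart from PD and excludes it from response.

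Counting relapse for DOR and DoCR would also remove the conflict if stated consistently and flagged as a difference from protocol 9.4. If PFS keeps footnote 4, DOR and PFS would then have different events.

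Either way, add Relapse to the list of adequate assessments after Table 5, so that a relapse visit is not treated as a missed assessment.

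**Table 4.** Remove the discontinuation condition and footnote 2 from the progression and death event rows. Censor patients alive without progression, on or off treatment, at the last adequate assessment. Keep the rules for new anti-cancer therapy and for two or more missed assessments. A sensitivity analysis with the 28-day limit is optional.

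**Cost.** SAP wording and one sensitivity run, or two with the optional one. Under PD-or-death, a relapsed patient who starts new therapy is censored, which may be informative; the sensitivity analysis shows how much. Some off-treatment events will still be censored because standard-of-care visits are sparse.
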